By my signature, I agree to personally supervise the condu- site and to ensure its conduct is in compliance with the pro- Institutional Review Board (IRB)/Ethics Committee (EC) p Celgene representatives, the Declaration of Helsinki, Interr Harmonisation (ICH) Good Clinical Practices Guidelines, a governing the conduct of clinical studies.	ct of this study at my study tocol, informed consent, procedures, instructions from national Conference on and local regulations

PROTOCOL SUMMARY

Study Title

A Phase 2, Randomized, Double-Blind, Placebo Controlled, Dose Range Finding Study to Assess the Efficacy and Safety of Intramuscular Injection of Human Placenta-Derived Cells (PDA-002) in Subjects With Diabetic Peripheral Neuropathy

Indication

This study will investigate the efficacy and safety of intramuscular (IM) injections of PDA-002 in subjects who have diabetic peripheral neuropathy (DPN) as a co-morbidity of Type 2 diabetes.

Objectives

The primary objective of the study is to assess the efficacy of PDA-002 versus placebo in subjects with DPN, based on the change from baseline in epidermal nerve histology at 6 months. The secondary objective of the study is to assess the safety and tolerability of IM administration of 2 different doses of PDA-002 or placebo in subjects with DPN.

The key exploratory objectives of the study are to assess potential treatment effects of IM administration of PDA-002 in subjects with DPN as measured by changes from baseline in:

- Epidermal nerve histology at 3 months
- Lower limb microvascular oxygenation
- Vascular reactivity
- DPN signs and symptoms
- Motor and sensory nerve conduction and autonomic function
- Health-related quality of life
- Vascular and immune, biomarkers, and laboratory parameters
- Assessment of the systemic versus local efficacy of PDA-002

Study Design

This is a Phase 2, randomized, double-blind, placebo-controlled, dose range finding study in subjects with DPN. The study will enroll approximately 24 subjects. Subjects will be randomized to receive one of 3 treatments: PDA-002 (3×10^6 cells), PDA-002 (30×10^6 cells), or placebo (vehicle control) in a 1:1:1 randomization approach. Investigational product (IP) or placebo will be administered monthly (3 administrations total; Study Days 1, 29, and 57). Subjects will be evaluated for efficacy and safety for approximately one year from the day of the last IP administration.

Study Population

The study population includes subjects with Diabetic Peripheral Neuropathy due to Type 2 diabetes mellitus (DM) as defined by the ADA or WHO criteria (Appendix A).

Length of Study

Subjects are expected to participate in the study from screening (Day 28) to 1 year after the -last IP injection.

Subjects will undergo a Screening Period of up to 28 days. During the Screening Period eligibility will be confirmed and baseline assessments will be performed. Subjects will then enter a 6 month Treatment Period consisting of 8 study visits. During the Treatment Period, IP will be administered on Study Days 1, 29, and 57, and efficacy and safety evaluations will be performed as outlined in the Table of Events (Table 1). Subjects will then enter a Follow-up Period. The Follow up Period will consist of bi-monthly study visits to continue to assess safety and longer-term efficacy.

End of Trial

The End of Trial is defined as either the date of the last visit of the last subject to complete the post-treatment follow-up, or the date of receipt of the last data point from the last subject that is required for primary, secondary and/or exploratory analysis, as prespecified in the protocol, whichever is the later date.

Study Treatments

Subjects will be randomized 1:1:1 to receive one of the following dose levels of IP:

- PDA-002 Dose Level 1: 3 x 10⁶ PDA-002 cells administered IM on Study Days 1, 29, and 57.*
- PDA-002 Dose Level 2: 30 x 10⁶ PDA-002 cells administered IM on Study Days 1, 29, and 57.*
- Placebo (vehicle control) subjects will receive placebo (vehicle control) administered in the same manner and at the same time points as the PDA-002 dosing groups.

*Subjects will be dosed in the same leg. The leg of injection will be the leg with the lowest combined qualifying NTSS-6 and UENS and NIS-LL score. In the case of a subject with an equal score for both legs, the choice of the leg to inject is at the discretion of the investigator.

PDA-002 and placebo (vehicle control) units will be shipped to the study sites as cryopreserved units and will be thawed and filled into syringes prior to IM injection.

Overview of Key Efficacy Assessments

The following efficacy assessments will be performed as outlined in the Table of Events (Table 1).

The primary efficacy assessment is the evaluation of change from baseline in Epidermal Nerve Fiber Density (ENFD) at 6 months.

Efficacy will also be assessed in an exploratory manner by evaluating changes from baseline in the following:

- ENFD at 3 months
- Microvascular oxygenation of the lower limbs by Hyperspectral Imaging (HSI)

- Vascular reactivity by Laser Doppler Iontophoresis and Nerve Axon Reflex measurements.
- The 6-item Neuropathy Total Symptom Score (NTSS-6) assessment
- The Neurological Impairment Score of the Lower Limb (NIS-LL)
- The Utah Early Neuropathy Scale (UENS)

Additional efficacy signals indicating changes in motor and sensory nerve conduction and autonomic function as evaluated by:

- Nerve conduction studies
- Quantitative Sudomotor Axon Reflex Testing (QSART). QSART is a measurement of autonomic involvement by evaluating postganglionic sudomotor function deficits in the foot, distal leg, and distal thigh.

Changes in health-related quality of life (QOL) will be assessed by the Norfolk QOL-DN.

Various experimental biomarker analyses will be performed to assess changes in the vascular and immune profile. Samples for biomarker analyses will include blood and epidermal tissue. In addition, an assessment of the systemic vs. local efficacy of PDA-002 will be evaluated.

Overview of Safety Assessments

Safety and tolerability will be assessed by the type, frequency, and severity of adverse events (AEs). As such, the following safety assessments will be performed as outlined in the Table of Events (Table 1).

- Assessment of adverse events and serious adverse events (SAEs)
- Physical examinations including complete neurological examinations and vital signs
- Clinical laboratory tests including chemistry, hematology, urinalysis, evaluation; urine pregnancy testing if applicable
- Twelve-lead electrocardiogram (ECGs)
- Retinal assessments
- Concomitant medications and procedures
- Immunological assessments
 - Anti-human leukocyte antigen (HLA) antibodies

Sample Size and Power Considerations

The sample size of 24 subjects total, 8 per treatment arm, was selected in order to provide preliminary efficacy and safety information in a randomized, double-blind fashion. The study is designed to provide an estimation of the treatment effect of active therapy and placebo to plan a sample size for the next study.

Based upon a previous study (Jacobs, 2011), the mean ENFD was 1.56 fibers/mm at baseline and 3.07 fibers/mm after 6 months of treatment with a standard deviation of 1.5 fibers/mm for the mean increase. Assuming the same treatment effect is observed from baseline, the sample size of

16 subjects actively on therapy resulting from combining the 2 active arms has a 96% power to detect a similar mean change at 6 months from baseline, with a two-sided test and a Type I error rate set at 0.05. Assuming the subjects treated with placebo would not have a change from baseline, the study has 60% power to detect similar differences between placebo and active therapy with PDA-002, with a two-sided test and a Type I error rate set at 0.05.

Efficacy and Safety Analyses

The planned efficacy and safety analyses will be fully described in a comprehensive SAP.

The efficacy analyses will also include a descriptive assessment of the exploratory objective to evaluate whether the treatment effect of PDA-002 is systemic or local. This will be done by taking into account the intersubject variability between measurements taken from the left and the right leg.

TABLE OF CONTENTS

TITLE H	PAGE	1
PROTO	COL SUMMARY	5
1.	INTRODUCTION	
2.	STUDY OBJECTIVES	
2.1.	Primary Objective	
2.2.	Secondary Objective	
2.3.	Exploratory Objectives	
3.	STUDY ENDPOINTS	
3.1.	Primary Endpoint	
3.2.	Secondary Endpoint	
3.3.	Exploratory Endpoints	
4.	OVERALL STUDY DESIGN	
4.1.	Study Design	
4.2.	Study Design Rationale	
4.3.	Study Duration	
4.4.	End of Trial	
5.	TABLE OF EVENTS	
6.	PROCEDURES	
6.1.	Study Entry/Screening Period (Visit 1)	
6.2.	Treatment Period (Visit 2 through Visit 9)	
6.3.	Follow-Up Period	
6.4.	Efficacy Procedures	
6.5.	Safety	
6.5.1.	External Data Monitoring Committee	
7.	STUDY POPULATION	
7.1.	Number of Subjects and Sites	
7.2.	Inclusion Criteria	
7.3.	Exclusion Criteria	
8.	DESCRIPTION OF STUDY TREATMENTS	
8.1.	Description of Investigational Product	
8.2.	Treatment Administration and Schedule	

PDA-002 Protocol CCT-PDA-002-DPN-001

821	Discontinuation	38
822	Overdose	
8.2.2.	Method of Treatment Assignment	
8.J. 8.4	Packaging and Labeling	39
8.5	Investigational Product Accountability and Disposal	39
8.6	Investigational Product Compliance	40
8.0. 8.7	Blinding	
0.7.	CONCOMITANT MEDICATIONS AND PROCEDURES	
9. Q 1	Permitted Concomitant Medications and Procedures	
9.1. 9.2	Prohibited Concomitant Medications and Procedures	
0.2	Required Concomitant Medications and Procedures	

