The doses selected for this study are based upon the effective doses adjusted for body weight that were administered in the previously described hind limb ischemia (HLI) animal models, as well as the dosing in the Phase 1 study PDA-002-DFU-001. Data on the first 3 dose cohorts of the Phase 1 study in which subjects were administered 3 x 10^6 cells, 10×10^6 cells and 30×10^6 cells on Days 1 and 8 demonstrated that the doses were well tolerated with no reported dose limiting toxicity (DLT). To date based upon the observed safety profile from the Phase 1 study, no new risks have been identified for PDA-002 that would preclude dosing in the Phase 2 studies.

For this study, subjects will be randomized to receive PDA-002 or placebo in one lower extremity in a blinded manner. Although PDA-002 is being administered IM, it is unclear if the therapeutic effect is localized to the area of injection or systemic. In pre-clinical HLI studies, the therapeutic effect of PDA-002 was similar in animals administrated the IM and intravenous (IV) formulation. The mechanism of action of PDA-002 is due to a modulation of the immune system from a pro inflammatory to anti-inflammatory state that facilitates angiogenesis both in the area directly in contact with PDA-002 along with other areas that may be affected by inflammation and ischemia. Since DPN causes a symmetrical dysfunction to the nerves of the lower extremities, assessments of nerve function as well as changes in neurologic signs will be assessed in both legs in order to determine if the therapeutic effect of PDA-002 is local vs. systemic.

The dosing schedule of PDA-002 in this study will be 3 repeated monthly administrations. The schedule is based on the safety of 3 repeat IM doses of PDA-002 demonstrated in animal studies. Please refer to the Investigator's Brochure for detailed information concerning the available pharmacology, toxicology, drug metabolism, clinical studies, and AE profile of PDA-002.

One additional design feature of this study is that while PDA-002 is injected into one leg, both legs are checked for changes in neuropathy signs and symptoms. This will enable determining if the effects of PDA-002 on DPN are limited to the area in which the cells are injected, or the effect is systemic.

Figure 1: Overall Study Design

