6-item Neuropathy Total Symptom Score (NTSS-6): The NTSS-6 questionnaire is used to evaluate the frequency and intensity of neuropathy sensory symptoms identified by subjects with DPN (ie, numbness and/or insensitivity, prickling, and/or tingling; burning pain; aching pain and/or tightness, sharp shooting lancinating pain and allodynia and/or hyperalgesia). Symptoms are graded based on the experience of the subject during the past 24 hours. Each symptom question can be assigned a maximum score of 3.66 points. The symptom scores are summed, and the total score can range from 0 points to 21.96 points. A higher score indicates greater disability.

Neurological Impairment Score of the Lower Limb (NIS-LL): The NIS-LL is an assessment tool composed of a sensory subscore (which evaluates sensory perceptions to touch, prickling pain, vibration, joint position, and to 1 gram and 10 gram monofilaments), and a motor subscore (which evaluates muscle strength, muscle wasting, and deep tendon reflexes) in the lower limbs. The scale is additive for all deficits and is applied in a bilateral manner for each modality tested. The subscores are totaled and can range from 0 points (normal neurological function) to 88 points (absence of all motor, sensory, and reflex activity). An increase of 2 points is clinically significant.

Utah Early Neuropathy Scale (UENS): The UENS uses a physical examination specific to early sensory predominant polyneuropathy which emphasizes severity and spatial distribution of sharp sensory loss in the foot and leg. The total score can range from 0 to 42. A higher score indicates greater disability.

Electro physiologic Nerve Conduction Studies: Nerve conduction studies allow for the quantification of the conduction amplitude, velocity, and latency of the tibial and peroneal nerves, and the amplitude and latency of the sural nerve. Reduction of amplitudes of recorded responses generally indicates a loss of axons. Nerve conduction will be measured in both lower limbs.

Quantitative Sudomotor Axon Reflex Testing (QSART): QSART is a measurement of autonomic involvement by evaluating postganglionic sudomotor function deficits in the foot, distal leg, and distal thigh.

Patient Global Impression of Change in Neuropathy (PGICN): The PGICN is a subject's self assessment to describe and change in symptoms of neuropathy such as pain, tingling, or numbress.

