8.2. Treatment Administration and Schedule

Investigational product (IP) will be administered on Study Days 1, 29 and 57. Thawing of the IP should not begin until it is confirmed that the subject meets the inclusion/exclusion criteria. Investigational product thawing will be performed by qualified site personnel according to the instructions in Appendix E. Three 3 mL syringes will each be filled with 1.5 mL of IP, and then capped. Syringes will be masked to preserve blinding, and transferred to the personnel administering the injections.

Subjects will receive IP administered as fifteen 0.30 mL injections (approximately 4.5 mL total) in one leg. The target region is suggested to be below the knee and above the ankle. Injections are suggested to be at least 1 cm apart horizontally and laterally and at a depth of approximately 1 to 4 cm. It is suggested that they be administered in a pattern of 3 x 5 injections around the leg, and injections should not be near a blood vessel. The administrator will be blinded to treatment.

PDA-002 is not intended for intravenous administration. When the injection is given, the syringe should be aspirated to avoid inadvertent venous administration. If any blood is aspirated into the syringe, the needle is to be pulled out a little, and the syringe re-aspirated. If no blood is seen, the IP may be injected.

Vital signs (including heart rate, respiration, blood pressure, body temperature) will be monitored prior to starting the injections and at 1 and 2 hours (\pm 15 minutes) after completion of

the injections. Blood samples for tryptase and histamine, coagulation assessments, and exploratory biomarkers will be collected as indicated in the Table of Events (Table 1).

The investigational centers must also offer appropriate supplemental services that support clinical care to ensure that the protocol specified IP administration and monitoring will be followed.

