10.6. Efficacy Analysis

The planned analyses will be fully described in a comprehensive SAP.

The primary efficacy analysis will be an evaluation of change from baseline in ENFD at 6 months following treatment with either dose of PDA-002 or placebo. Results will be used to assess the proof of concept for further study of PDA-002 in subjects with DPN. The analyses will also take into account the possible inter-subject variability of measurements evaluated in both the treated leg (with active or placebo) and the other leg that received placebo.

Changes in the various exploratory efficacy endpoints including within subject differences between left and right leg measurements will be evaluated using descriptive statistics.

In general, exploratory endpoints that are categorical will be examined using descriptive summaries such as counts and percentages, whereas exploratory endpoints that are continuous will be examined using means, standard deviations and medians. The results of the exploratory analyses will allow for better definition of the clinical efficacy endpoints.

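### The injected-leg rule relies on per-leg scores the protocol never defines, and leg differences in the selecting scores will drift unless referenced to placebo

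*Combined protocol and SAP*

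**What the plan says.** The Protocol Summary (Study Treatments, footnote) assigns the injections to "the leg with the lowest combined qualifying NTSS-6 and UENS and NIS-LL score". A second sentence covers ties: where both legs score the same, the investigator chooses. Both sentences presuppose one score for each leg.

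Section 6.4 describes the three scales as follows.
- **NTSS-6:** "The symptom scores are summed, and the total score can range from 0 points to 21.96 points. A higher score indicates greater disability".
- **NIS-LL:** "The scale is additive for all deficits and is applied in a bilateral manner for each modality tested". The total runs from 0 (normal) to 88.
- **UENS:** a total from 0 to 42, with higher again meaning more disability.

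Inclusion criterion 5 lets a subject qualify on UENS, on NIS-LL or on both. Table 1 schedules all three scales at screening and next at Day 29.

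The dosing text does not repeat the rule. Section 8.2 says "Subjects will receive IP administered as fifteen 0.30 mL injections (approximately 4.5 mL total) in one leg", and Section 4.1 and Appendix E likewise do not say how the leg is chosen.

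Section 4.2 makes the comparison of the two legs the means of telling a local from a systemic effect. Section 10.6 plans that changes in the exploratory endpoints, "including within subject differences between left and right leg measurements will be evaluated using descriptive statistics".

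**The concern.** There are two separate difficulties.

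The first is definition. The footnote compares the legs on a quantity that Section 6.4 does not supply. The word qualifying has no stated meaning for a leg, no weighting is given for adding scales of different range, and the choice of the lower score is unexplained. Sites could apply the rule differently, so the injected leg would not mean the same thing in every subject.

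The second is statistical. A leg picked because its screening score was the lower of two was picked partly on measurement error. That error does not repeat at follow-up, and the same screening value serves as baseline. The injected leg's score is then expected to rise relative to the other leg, which looks like relative worsening, even if the product does nothing. A leg comparison made within the PDA-002 arms would be tilted against a local benefit on those scores.

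**Working it through.** **The plan's own figures.** Section 10.3 states 96% and 60% power for ENFD. The effect is 3.07 − 1.56 = 1.51 fibers/mm with SD 1.5, two-sided 0.05.
- One sample, n = 16: noncentrality 1.51/1.5 × √16 = 4.03, power 96.4% by noncentral t.
- Two samples, 16 versus 8: 1.51/(1.5 × √(1/16 + 1/8)) = 2.32, power 60.4%.

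Both reproduce, and neither uses the leg scores. The documents attach no figure to the leg rule itself.

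**Is there a leg-level score?** Suppose NTSS-6 is one subject total N and the leg-specific parts are a(L) and a(R). The leg scores are N + a(L) and N + a(R), and their difference is a(L) − a(R). NTSS-6 drops out, so the choice rests on UENS and NIS-LL subtotals. Section 4.2 says signs are assessed in both legs, so such subtotals may be recorded, but no section defines them.

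**Expected drift, one selecting scale.** Let D be the left-right difference at screening, S its SD and r its repeatability. S and r are assumptions, because the documents give neither. Take D as normal with mean 0.
- Injected minus other at screening is −|D|, with mean −√(2/π) × S = −0.798 S.
- At follow-up with no effect, its expectation is r times that.
- Expected change = (1 − r) × 0.798 × S, in the direction of relative worsening of the injected leg.

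**Two selecting scales.** If two independent scales with equal S are summed, each correlates 1/√2 = 0.707 with the sum. The drift per scale is (1 − r) × 0.798 × 0.707 × S = (1 − r) × 0.564 × S.

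With S = 2 points (closed form, confirmed by simulation):

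| r | One scale selects | Two independent scales, per scale |
|---|---|---|
| 0 | 1.60 | 1.13 |
| 0.5 | 0.80 | 0.56 |
| 0.8 | 0.32 | 0.23 |

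For one scale with S from 1 to 4 and r from 0.2 to 0.8, the range is 0.16 to 2.55 points.

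**How visible it would be.** As an illustration only, a paired test of injected versus other leg in 16 subjects at nominal 5%, with S = 2 and no effect, rejected in about 73%, 37% and 16% of simulated trials at r = 0, 0.5 and 0.8 with one selecting scale. With two independent scales it rejected in about 37%, 20% and 10%. The same leg difference compared between 16 PDA-002 and 8 placebo subjects had mean drift of about 0 and rejected in about 5% throughout.

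**ENFD.** ENFD does not select the leg. If its measurement error is independent of the errors in the scores, its expected drift is 0. With an assumed error correlation of 0.3 and an assumed SD of 1.0 fibers/mm for its leg difference, simulation gave about 0.08 to 0.15 fibers/mm.

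**The case against.** Much of the case on the other side stands.
- **The rule is not strictly unworkable.** A subject-level NTSS-6 cancels between legs, and NIS-LL is examined on each side. What is missing is a definition.
- **No leg test is planned.** Section 10.6 is descriptive, so the rejection rates above show how large the drift is relative to noise. They are not an error rate of this trial.
- **Symmetry cuts both ways.** Section 4.2 argues "Since DPN causes a symmetrical dysfunction to the nerves of the lower extremities". That suggests low repeatability of the leg difference, but also a small SD and more ties, and tied legs are not selected on score.
- **The comparator may already be intended.** Section 2.3 frames the exploratory objectives against placebo, and detail is left to a separate SAP. But Section 10.6 does not name the contrast, and a literal left-minus-right summary would mix subjects injected on different sides.

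A reader might infer three stronger things that the documents do not support.
- **That the direction is a mistake.** Nothing says the more affected leg was intended.
- **That the whole two-leg comparison, ENFD included, is biased.** The drift belongs to the scores that choose the leg.
- **That the injected leg can hold at most 5 NIS-LL points, half of the upper eligible value of 10, and so has little room to improve.** That bound applies to the leg with the lower NIS-LL, whereas the leg is chosen on a combined score. The 2-point change called clinically significant in Section 6.4 is a worsening of the total, not of one leg.

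**Conclusion.** The point holds in limited form. The footnote and Section 6.4 do not fit together: the leg-level score is undefined and the direction unexplained. Separately, injected-versus-other differences in UENS and NIS-LL will show some spurious relative worsening of the injected leg if read within the PDA-002 arms. At an assumed SD of 2 points and repeatability of 0 to 0.8, this is about 0.3 to 1.6 points with one selecting scale, or about 0.2 to 1.1 points per scale with two independent ones. These figures rest on assumed values and on continuous differences without ties, so they indicate scale only. The existence and sign of the drift follow from the rule whenever repeatability is below 1. Measures that do not select the leg are not biased by this alone. The primary between-arm ENFD comparison and the stated 96% and 60% power are unaffected. What is at stake is an exploratory objective, and the remedy is cheap.

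**What to change.** 1. **Reconcile the Summary footnote with Section 6.4.** State how each scale yields a leg-level score, how the scores are combined, and what qualifying means. Have the clinical team confirm the intended direction. Cross-refer to the single rule from Sections 4.1 and 8.2 and Appendix E. In the same edit, reconcile the Section 10.6 remark that the other leg received placebo with the single-leg injection in Section 8.2.
2. **Name the contrast in Section 10.6 and the SAP.** For each bilateral measure, take the change in the injected leg minus the change in the other leg, not left minus right. Estimate it in PDA-002 subjects minus placebo subjects with a confidence interval, adjusted for the baseline leg difference. The Summary says placebo is given in the same manner, so the selection drift is the same in every arm and cancels in expectation.

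The cost is a wording amendment, one extra contrast and some precision. With s the SD of the leg-difference change, the standard error goes from s × √(1/16) = 0.250 s within the pooled PDA-002 arms to s × √(1/16 + 1/8) = 0.433 s against placebo. That is about 1.7 times as wide before any gain from baseline adjustment. The within-arm summaries can still be shown beside it, labelled as carrying the selection drift for UENS and NIS-LL.
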